### **Research Hypothesis**

- a. **Null hypothesis:** There is no difference between the SADL-eM and the standard care delivered to inpatients with SCI in a rehabilitation setting.
- b. **Alternative hypothesis:** The implementation of a SADL-eM delivered to inpatients with SCI in a rehabilitation setting has a significant impact on their ADL.

### **Methodology**

#### **Study Design**

**Please insert Figure 1 (Study Flow Diagram) here**

This is a parallel, single blinded (assessor) randomized clinical trial (RCT) with a pre-/post-test to evaluate a hypothesis of cause-and-effect relationship. This study uses the Consolidated Standards of Reporting Trials (CONSORT) statement as the proposed standard for the reporting of parallel-group RCTs (Moher et al., 2010).

#### **Participants, sampling method, sample size, and setting**

Participants in the study will be SCI inpatients from the Gaza Strip, both genders, of any cause or type of SCI, and age 18-65 years. They will be recruited from admitted inpatients in one of the three rehabilitation settings (Hamad, ElWafa, or ElAmal Rehabilitation hospitals). Readmissions will be included in the study if they are eligible. These three inpatient rehabilitation hospitals are located in the Gaza Strip of Palestine and are private sector health services. They provide comprehensive rehabilitation services. Their rehabilitation teams include physical rehabilitation doctors, rehabilitation nurses, physiotherapists, occupational

therapists, speech therapists, clinical dietitians, psychologists, social workers, orthoptists, and community-based rehabilitation workers. The sample size was determined to detect an effect size of 15%, power of 80%, 5% margin of error, and 95% Confidence Interval (CI). The study sample of 90 SCI individuals will be randomized to two groups, conventional therapy (n1=45) and intervention/SADL-eM & conventional therapy (n2=45) using a simple randomization approach. Inclusion and exclusion criteria are listed in Box 1.

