The purpose of the SADL-eM is to serve as a treatment tool during inpatient rehabilitation. Over the first week of admission of each person with SCI in each facility, a research clinical supervisor will recruit study participants based on the study eligibility criteria, obtain consent, and assign each consenting patient to one of the two study groups. They will then provide each participant in the intervention group with a SADL-eM hard copy, and explain the purpose of the manual and how to use it. The manual will be reviewed by the treating occupational therapist and the person with SCI during their treatment sessions. During occupational therapy sessions, the therapist will refer to the relevant chapter of the manual. The therapist will also indicate to the participants which parts of the manual are not relevant to them (based on their gender, driving status, or level of SCI). Participants' queries on the content of the manual will be answered by the treating occupational therapist. The therapist will include the manual in as many SADL-eM educational sessions as required, but not less than three sessions per week with 15 minutes per session. The minimum level of clinical experience of each treating occupational therapist will be two years. Good Arabic language comprehension, and the ability to read and write is mandatory for both therapists and patients. No other special skills or experience are required.

The participants will keep the manual to review after sessions and after discharge from the inpatient rehabilitation setting. For the purposes of the study, blinding and bias reduction, the therapists and the participants in the intervention group must not share any part of the manual or information included with other patients or staff. The research assistant who performs data collection, the clinical supervisor, and occupational therapy team will be invited for informational session prior to data collection in each of the participating settings. The informational session will focus on the study purpose, recruitment, eligibility criteria, use of

the SADL-eM, roles, bias reduction, and blinding. Use of data collection tools will take place in a separate session with the research assistant. The principal researcher will answer all questions of the research team during informational sessions and during the research.

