## **Data Collection**

All admitted SCI patients will be evaluated by the research supervisor in the setting for eligibility within three days of admission to the inpatient rehabilitation setting, until the desired sample size is reached. Eligible individuals will sign a consent form and then be assigned randomly to one arm of the study by the research supervisor. The allocation sequence will be concealed from patients, therapist and, assessor. The data about exposure to the educational intervention will be collected by a separate research assistant by phone and will be concealed

from the assessor. Each occupational therapy department will assign four therapists to follow up the trial cases – two for the intervention and two for control group. All the staff in the occupational therapy department, participants, and assessors will be requested not to discuss the trial and intervention material between them. The importance of concealing any information until the end of the study will be explained. Study participants are not allowed to switch between occupational therapists or study arms. They will be asked not to participate in other educational interventions (peer or external) related to their rehabilitation or seek treatment outside their trial. The head of occupational therapy department within each rehabilitation setting will supervise participants and assigned occupational therapists in both study arms to reduce contamination bias such as sharing intervention content with the control group, sharing similar time and space of occupational therapy sessions, and exchange of therapists.

Contamination bias due to already existing background and/or receipt of additional educational interventions will be measured within each arm of the study (Chi-Square test to compare the progress means). However, no case will be eliminated from statistical analysis due to contamination bias.

The study will adopt approaches to prevent loss of participants to follow-up by making questionnaires as easy to complete as possible, providing incentives in the form of a free copy of the educational manual for the control group, and explaining the importance of the study (Magill, et al., 2019).

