### 46 Random Numbers

43 13 12 81 57 53 75 09 68 07 74 35 14 90 31 25 66 56 59 80 86 20 58 60 77 03 85 45  
73 50 84 55 19 36 33 42 16 70 01 91 28 34 39 24 69 04

**Specs:** This table of 46 random numbers was produced according to the following specifications: Numbers were randomly selected from within the range of 1 to 92. Duplicate numbers were not allowed. This table was generated on 8/19/2020.

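### The named randomization method does not match the 46-of-92 list, and nothing says how three hospitals share that list or adjusts for hospital

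*Combined protocol and SAP*

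**What the plan says.** Three parts of the document describe the allocation.

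- **Size and method** (Participants, sampling method, sample size, and setting): "The study sample of 90 SCI individuals will be randomized to two groups", specified as "conventional therapy (n1=45) and intervention/SADL-eM & conventional therapy (n2=45) using a simple randomization approach". On sites: "They will be recruited from admitted inpatients in one of the three rehabilitation settings". No target per hospital is given.
- **The list** (46 Random Numbers, and the caption below it): "Numbers were randomly selected from within the range of 1 to 92" and "Duplicate numbers were not allowed". The caption identifies the 46 numbers as the intervention group. The list has no hospital or stratum label.
- **Who assigns and who treats:** the SADL-eM section states that "in each facility, a research clinical supervisor will recruit study participants", obtain consent and assign the arm. Data Collection adds that "Each occupational therapy department will assign four therapists to follow up the trial cases", two for each arm, and bars patients from changing therapist or arm. It conceals the sequence from patients, therapists and assessor. The research supervisor, who assigns, is not on that list.

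Data Analysis names repeated measures ANOVA and linear mixed models to compare the arms, with no hospital or therapist term. No section mentions stratification, blocking, separate lists, or a rule for sharing the numbers among hospitals.

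**The concern.** Simple randomization tosses a fair coin for each patient and does not fix arm sizes. A draw without replacement does fix them. The plan names the first method, states a target that only the second can guarantee, and prints a list sized for 92 rather than 90. The protocol commits to CONSORT reporting, under which the sequence-generation method must be stated correctly; as written it would be reported wrongly.

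The second issue is the hospital. It is the unit through which the intervention is delivered, since each department supplies its own therapist pairs. Hospitals may differ in case mix and usual care. If the arms are uneven within a hospital, hospital differences add noise to the arm comparison, and the planned model has no term to remove it. The silence on sharing matters in practice too: with several supervisors and one list, nothing ensures that each slot from 1 to 90 is used once and in order, which is the condition under which the list yields the stated split.

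**Working it through.** **Inputs from the document:** N = 90, 45 per arm, three hospitals, the printed 46 numbers, two therapists per arm per hospital. **Assumed, because not stated:** hospital sizes of 30/30/30 or 15/30/45, and that the trial has exactly its planned 80% power at a balanced 45/45.

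**1. Can the list give the stated split?** The list has 46 distinct numbers. All but one (91) are at or below 90, so slots 1 to 90 hold 45 intervention and 90 − 45 = 45 control places. The stated 45/45 is reproduced. Slots 1 to 92 give 46/46. In advance, a 46-of-92 draw gives 45/45 at slot 90 with probability C(90,45) × 2 / C(92,46) = 50.5%, and otherwise 44/46 or 46/44.

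**2. Balance within hospitals.** I simulated 46-of-92 draws, spread the first 90 slots over the hospitals without regard to arm, and counted trials in which at least one hospital was uneven.

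| Assumed sizes | Some hospital 60:40 or worse | Some hospital 2:1 or worse |
|---|---|---|
| 30/30/30 | 51% | 11% |
| 15/30/45 | 68% | 29% |

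**3. What an uneven hospital costs locally.** In a hospital of 30, relative to 15/15:
- 18/12: (1/18 + 1/12) / (2/15) = 1.042, so variance is 4.2% higher.
- 20/10: (1/20 + 1/10) / (2/15) = 1.125, so variance is 12.5% higher, and the smaller arm's two therapists have about 10/2 = 5 patients each instead of 15/2 = 7.5.

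**4. What it costs the trial.** For an arm contrast adjusted for hospital, the information is the sum over hospitals of n1 × n0 / n. Perfect balance gives 90/4 = 22.5, so the variance inflation is 22.5 divided by that sum. Over the simulated draws:
- Mean inflation is 2.4% under both sets of sizes.
- The 95th percentile is about 7% under both.
- If power is 80% at perfect balance, it is about 79% at the mean and about 77% at the 95th percentile.

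**5. The printed list, if cut into consecutive thirds.** Slots 1–30, 31–60 and 61–90 give 14/16, 17/13 and 14/16 (intervention/control). The information is (14×16 + 17×13 + 14×16)/30 = 669/30 = 22.3, an inflation of 22.5/22.3 = 1.009, or 0.9%.

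**6. After the fix.** With blocks of 4 and 6, an unfinished block leaves a difference of at most 3 in a hospital. Three differences of 3 would need three odd hospital sizes, which cannot sum to 90, so the overall difference is at most 8 (41/49). Variance rises by (1/41 + 1/49) / (2/45) = 1.008, and power is 79.7% against 80.0%.

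**The case against.** The strongest reply is that this is a labelling error with a small consequence. Much of that stands. The list fixes the arm sizes and its first 90 slots give 45/45. Chance imbalance under valid randomization does not bias the estimate in expectation; it costs precision, and a hospital term recovers most of what matters. The 60:40 threshold is a low bar, since 18/12 costs that hospital only 4.2%. The therapist pairs do not by themselves argue for stratification: therapists are nested in arm at any split, and balancing hospitals leaves that unchanged. Blocks also carry a price, because later assignments in a small hospital become easier to guess when therapists and patients know the arm.

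A reader might infer that the 45/45 split is unattainable, because true simple randomization of 90 gives exactly 45/45 with probability only C(90,45)/2^90 = 8.4%. The document does not support that reading: the appended list shows that coin-tossing is not the scheme in hand. A reader might also infer that one list is run across all hospitals without regard to site. That rests on silence; the plan does not say how the numbers are distributed.

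What survives is that the text and the list disagree, that the operating rule across hospitals is missing, and that the analysis has no hospital term to absorb whatever imbalance results.

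**Conclusion.** The point holds as a misnamed method, a mismatch between 46/92 and 45/90, and an unspecified procedure across hospitals combined with an analysis that ignores hospital. It does not show a serious threat to overall balance or power, nor a biased comparison. A badly uneven hospital is a moderate risk (about 11% to 29% for 2:1 or worse), and the expected loss is about 2.4% of variance, about 7% in an unlucky draw. These figures depend on the assumed hospital sizes and on the 90 slots being spread over hospitals without regard to arm. The inflation figures apply to a hospital-adjusted contrast, which the plan does not yet specify. The change is worth making because it is cheap and makes the randomization reportable, not because the trial fails without it.

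**What to change.** Before recruitment starts:

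1. In the sample-size section, replace the reference to simple randomization with 1:1 randomization stratified by hospital, in permuted blocks of randomly varying size (for example 4 and 6), to a total of 90 and about 45 per arm.
2. Replace the printed 46-of-92 list with three newly generated lists, one per hospital, held away from the sites and not printed in the protocol.
3. In Data Collection, extend concealment to the research supervisor, so that each assignment is revealed only once that patient is enrolled.
4. In Data Analysis, add hospital as a term in the model comparing the arms. Stratifying without this would give standard errors that are too large if hospitals differ.

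If the existing list has already been used, state the method as a fixed-size draw, record how its numbers were shared among hospitals, and still add the hospital term.

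The cost is three lists, a few sentences and a way to release assignments from off site. Blocks are slightly more guessable in an open-label trial with small hospitals, which varying block sizes and concealed lists limit. Final arms may differ by a few patients (at most 8 with blocks of 4 and 6), with negligible effect on power. N stays at 90.

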**Please insert box 1 (inclusion and exclusion criteria) here**

### **Pilot study**

Pilot studies are small-sample, preliminary studies which aim to investigate the feasibility of a study. RCTs usually use pilot studies to improve feasibility and avoid crucial barriers (Bell, Whitehead, and Julious, 2018). A small number (15) of participants with SCI of any cause and of any type aged 18-65 years with a previous inpatient rehabilitation experience will take part in the pilot study. They will be selected from the 2019-2020 inpatient list of Hamad Rehabilitation Hospital. They will complete the Spinal Cord Independence Measure-Self Reported (SCIM-SR). A well-trained research assistant (physiotherapist) will administer the biographical data collection tool, the Spinal Cord Independence Measure-III (SCIM-III), the Private Religiousness Practices Scale, Organizational Religiousness Short-Form, and the domains of ADL covered by the educational manual including driving and community mobility, personal device care, health management and maintenance, Wudu, and Salat. The patients and the research assistant will comment on the tools employed and point out any problems with the tests' instructions, instances where items are not clear, and formatting and other typographical errors and/or issues. Each question measures performance/participation in ADL will be analyzed using the Cronbach's Alpha to test and improve reliability.

### **SCI ADL Educational Manual (SADL-eM)**

Both study groups will receive usual care. In addition, each participant in the experimental group will receive a copy of the SADL-eM from their occupational therapist with a short discussion about its importance and use.

The SADL-eM was developed by the authors following a systematic review (BLINDED FOR REVIEW) and user-led development project. A team of 54 Subject Matter Experts (SME) collaborated in a Participatory Action Research (PAR) project to develop the manual. The researchers used eight consecutive focus groups and Nominal Groups Technique (NGT) for

consensus. The manual production took 17 months and is to our knowledge the first comprehensive SCI ADL educational tool available in Arabic.

The SADL-eM includes three elements essential to the intervention, namely: knowledge, skills, and advice. The manual includes 92 A5 pages with six detailed sections: an Introduction and five chapters: (1) Rehabilitation team, (2) Activities of Daily Living, (3) Assistive devices, (4) Home environment adaptation, and (5) Knowledge guide. The SADL-eM uses text and illustrative pictures that are carefully selected for contextual relevance. The manual is simple, easy, and suitable for people with a non-medical background. However, good Arabic language comprehension, read and write is mandatory for users. No other special skills or experience are required.

The purpose of the SADL-eM is to serve as a treatment tool during inpatient rehabilitation. Over the first week of admission of each person with SCI in each facility, a research clinical supervisor will recruit study participants based on the study eligibility criteria, obtain consent, and assign each consenting patient to one of the two study groups. They will then provide each participant in the intervention group with a SADL-eM hard copy, and explain the purpose of the manual and how to use it. The manual will be reviewed by the treating occupational therapist and the person with SCI during their treatment sessions. During occupational therapy sessions, the therapist will refer to the relevant chapter of the manual. The therapist will also indicate to the participants which parts of the manual are not relevant to them (based on their gender, driving status, or level of SCI). Participants' queries on the content of the manual will be answered by the treating occupational therapist. The therapist will include the manual in as many SADL-eM educational sessions as required, but not less than three sessions per week with 15 minutes per session. The minimum level of clinical experience of each treating occupational therapist will be two years. Good Arabic language comprehension, and the ability to read and write is mandatory for both therapists and patients. No other special skills or experience are required.

The participants will keep the manual to review after sessions and after discharge from the inpatient rehabilitation setting. For the purposes of the study, blinding and bias reduction, the therapists and the participants in the intervention group must not share any part of the manual or information included with other patients or staff. The research assistant who performs data collection, the clinical supervisor, and occupational therapy team will be invited for informational session prior to data collection in each of the participating settings. The informational session will focus on the study purpose, recruitment, eligibility criteria, use of

the SADL-eM, roles, bias reduction, and blinding. Use of data collection tools will take place in a separate session with the research assistant. The principal researcher will answer all questions of the research team during informational sessions and during the research.

For the purposes of the current study, the SADL-eM will be provided during face-to-face individual occupational therapy sessions without any constraints regarding treatment area. It could be occupational therapy department, patient ward, and educational activities room. The face-to-face manual delivery does not require any infrastructure or special equipment.

The number of sessions, time allocated, and frequency are determined by each therapist and participant. Determinants may include participant's capabilities, potentials, and progress during treatment; and the scope of the service such as time allocated for each patient, therapist-patient ratio, and frequency of inpatient sessions. The therapist and the participant will continue to use the manual during treatment sessions until they decide there is no need for further use of the manual or the participant is discharged. Treating occupational therapists will retain records of any change or modification of the SADL-eM administration. The researchers will conduct a pilot study in a similar sample of 15 S people with SaCIs to improve the use of intervention and data collection tools.

Nonadherence to medical treatment in clinical trials of medical efficacy has serious consequences on the quality of research. It may obscure data collected and disrupt findings obtained (Quittner, et al., 2000). The steps to ensure adherence to the intervention during study include clearly defining the intervention, measuring, and then comprehensively reporting adherence to the intervention. Attendance records collected by the therapist (times, duration, and intensity of treatment; manual elements covered) and SADL-eM adherence therapist-report questionnaire will be used to measure and report adherence to the SADL-eM intervention. The manual will be made freely available on the Stellenbosch University website when the research is complete.

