The researchers will use the same outcome measures all through the study and with both of study arms. Biographical data will be collected by a research assistant once on the participant's admission and consent to participate. ADL data collection from each participant in the study will take place in a face-to-face interview twice (on admission before providing with the educational manual and 6 weeks later) using: (a) Patient-administered SCIM-SR and (b) Research assistant-administered SCIM-III, the Private Religiousness Practices Scale, Organizational Religiousness Short-Form, and the domains of ADL covered by the educational manual including driving and community mobility, personal device care, health management and maintenance, Wudu, and Salat. The data will be used to compare the results and means of both groups, answer the research question, and test the study hypothesis.

Polit, et al. (2001) pointed out that the validity of the experimental study can be threatened by history, selection, and maturation. This study finding's validity will be enhanced by concealing intervention group using a blinded assessor. The bias of sampling and contamination will be

minimized through randomization and assuring freedom of participation and anonymity of participants.

Objective data collected in clinical settings using valid and reliable tools is essential for evaluating the impact of an intervention (Polit, et al., 2001). The validity and reliability of the data collected and results of the study will be improved using standardized measurement tools such as SCIM-III and SCIM-SR.

**Biographical Data Collection Tool:** an English 24-item tool that captures demographic and socioeconomic data including age, gender, marital status, level of education, employment, monthly income, accommodation, diagnosis, and cause and type of SCI. The researchers developed the tool to be used in English version in this study.

**Spinal Cord Independence Measure-Self Reported (SCIM-SR):** a patient-reported 17-item tool that evaluates the ability of a person with SCI to perform specified activities independently, with assistance, or with assistive devices. The tool uses an ordinal scale.

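### The pre-trial briefing covers use of the SADL-eM and, as worded, is open to control-arm therapists and the outcome assessor: an avoidable contamination route and a possible threat to assessor blinding

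*Combined protocol and SAP*

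**What the plan says.** The section SCI ADL Educational Manual (SADL-eM) sets up a briefing in each participating hospital: "The research assistant who performs data collection, the clinical supervisor, and occupational therapy team will be invited for informational session prior to data collection". Its content is given in a sentence that runs over a page break: "The informational session will focus on the study purpose, recruitment, eligibility criteria, use of", continuing "the SADL-eM, roles, bias reduction, and blinding". One topic is held apart: "Use of data collection tools will take place in a separate session with the research assistant". No comparable separation is made for the manual.

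Immediately before the invitation, the same section says that therapists and participants in the intervention group "must not share any part of the manual or information included with other patients or staff".

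Under Data Collection, each occupational therapy department names four therapists for the trial, "two for the intervention and two for control group". Department staff, participants and assessors "will be requested not to discuss the trial and intervention material between them". The same section relies on "concealing intervention group using a blinded assessor" to protect validity, and it makes the research assistant the person who administers the SCIM-III and the other interviewer-administered scales. The SCIM-SR, named in the Abstract as the primary outcome, is completed by the patient.

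**The concern.** The intervention is largely information: a manual that conveys knowledge, skills and advice, worked through with an occupational therapist. Control patients are treated in the same departments by other therapists. If those therapists are briefed on how the manual is used, they can carry parts of it into usual care, intentionally or not. The control arm would then move towards the intervention arm and the estimated difference would shrink.

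The second issue is blinding. Study Design describes the trial as single blind, with the assessor as the blinded party, and no other blinding is claimed. The assessor is invited to a session whose agenda includes both the manual and the roles of the staff. If roles means who treats which arm, then knowing a patient's therapist is enough to know the patient's arm, because participants may not switch therapists.

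**Working it through.** **Step 1. Who attends.** The invitation names the data-collecting research assistant, the clinical supervisor and the occupational therapy team. The team is not qualified by arm. With two control therapists per department and three hospitals (Participants, sampling method, sample size, and setting), that is 2 × 3 = 6 control therapists, all of those assigned to the control arm. They are not named as attendees; their inclusion follows from the unqualified word team read with the staffing rule.

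**Step 2. What is covered.** Seven topics are listed: purpose, recruitment, eligibility, use of the SADL-eM, roles, bias reduction and blinding. The depth of the manual item is not stated.

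**Step 3. The rule beside it.** The no-sharing rule bars intervention therapists and participants from passing manual information to other staff. Control therapists are other staff. The session puts the use of the manual before them, so the two provisions need reconciling.

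**Step 4. What the safeguards reach.** Separate therapists, no switching, the no-discussion request and supervision by the head of department all act on sharing after the session. None addresses what was learned in it. The planned contamination check looks at existing background and additional education received, and it keeps every case. Keeping every case is right under the intention-to-treat analysis in Data Analysis, but it means contamination has to be prevented, because the analysis will not remove it.

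**Step 5. The assessor.** The allocation sequence is concealed from the assessor, and exposure data are collected by a different research assistant and withheld from the assessor. The briefing precedes data collection. Attendance therefore discloses no individual allocation. The remaining routes are the roles item, if it discloses therapist-to-arm assignment (the documents do not say), and, more weakly, recognition of cues at six weeks.

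**Step 6. Sensitivity of power to dilution.** The plan states an effect size of 15%, 80% power, a 5% level and 90 patients (45 per arm); sidedness is not stated and two-sided is assumed. The figure of 90 reproduces if 15% is read as Cohen's f = 0.15 for the group-by-time interaction in a repeated measures ANOVA with two groups and two time points. The correlation between the two measurements is assumed to be ρ = 0.5, as the documents give none:

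λ = f² × N × 2 / (1 − ρ) = 0.0225 × 90 × 2 / 0.5 = 8.10, with 1 and 88 degrees of freedom, giving power 0.804.

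Let c be the fraction of the effect lost to contamination. The documents give no value for c. Then λ is multiplied by (1 − c)². As a check that needs neither f nor ρ, start from the stated 80%: the normal noncentrality is 1.960 + 0.842 = 2.802, multiplied by (1 − c), and power is Φ(noncentrality − 1.960). Values are rounded after calculation.

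| Assumed c | Noncentrality | Less 1.960 | Power, normal | λ | Power, ANOVA |
|---|---|---|---|---|---|
| 0 | 2.802 | 0.842 | 0.80 | 8.10 | 0.804 |
| 10% | 2.521 | 0.561 | 0.71 | 6.56 | 0.717 |
| 20% | 2.241 | 0.281 | 0.61 | 5.18 | 0.615 |
| 30% | 1.961 | 0.001 | 0.50 | 3.97 | 0.504 |

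The two methods agree closely. The table shows what dilution from any source would do; it does not measure what this session would cause. The sample size statement mentions no allowance for dilution.

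**The case against.** The strongest reply is that the text supports less than a quick reading suggests.

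- A reader might infer that the session unblinds the assessor. It does not: blinding concerns each patient's arm, which a briefing before data collection cannot reveal, and both the allocation sequence and the exposure data are kept from the assessor. The assessor also already asks about the ADL domains that the manual covers, so keeping the assessor away from the manual item would not remove that knowledge. This stands. Only the roles item and possible cue recognition remain.
- A reader might infer that the content of the 92-page manual is taught to control therapists. The documents say only that its use is one of seven topics. The item could be logistical, and control therapists need some explanation of what must not be shared. This stands as a limit on wording. It does not dispose of the point, since nothing confines the item to logistics.
- The sponsor may have meant intervention therapists only. That is possible; if so, one qualifying phrase settles the contamination question.
- The dilution figures are not evidence about this session. Agreed. Control patients receive no manual during the study and none of the manual sessions, planned at no fewer than three a week of 15 minutes each. Both arms sharing a department is a separate route that a split briefing would not close.
- Any loss of assessor blinding would not directly touch the primary outcome, which the patient completes. Agreed, though the SCIM-III is listed among the primary objectives (item c).

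**Conclusion.** The point holds as a conflict in the plan that should be resolved before the briefings take place. Followed as written, on a plain reading, the plan briefs all six or so control therapists on use of an information-based intervention that the preceding sentence says must not reach other staff. The expected direction of any resulting bias is towards no difference. Its size cannot be derived from the documents, and the power figures for 10% to 30% dilution are illustrations under assumed leakage.

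For the assessor, the conclusion is a possible threat to blinding, conditional on the roles item disclosing therapist-to-arm assignment. It concerns mainly the SCIM-III and the other interviewer-administered scales. The documents do not support saying that the plan unblinds the assessor.

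The conclusion rests on one reading: that the unqualified occupational therapy team includes the control therapists.

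**What to change.** In the SADL-eM section, divide the briefing by audience:

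1. A common session for all staff on study purpose, recruitment, eligibility, bias reduction, blinding and the no-sharing rules.
2. A session on use and content of the SADL-eM for the intervention therapists and the clinical supervisor only, with a statement that control therapists and the outcome assessor do not attend.
3. Therapist-to-arm roles kept out of any session the assessor attends, including the common one.

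If the sponsor already intends the manual item for intervention therapists only, say so in the invitation sentence; item 3 is still needed.

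The cost is a few sentences and a split agenda, with no extra patients or staff. Separate sessions are evidently workable, because training on the data collection tools is already held apart. The one small downside is that a control therapist could not cover for an intervention therapist, an exchange that the Data Collection section already guards against.
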